4.2. Study Endpoints

The impact of the event-driven design is that we will continue to follow up until 92 first infection events have been observed in aggregate between Groups 1 and 4, and 72 first infection events have been observed in the aggregate of Groups 2 and 5 up to a maximum of 12 months of ADI. This clinical study was designed to capture positive *P. falciparum* infection events by PCR for at least 6 months of ADI (see section 10.5 for sample size calculation and presumed attack rate) but no longer than 12 months. If the aggregate numbers of first infection events have been reached between 6 and 12 months of ADI, the study endpoints will have been reached. The study will then be concluded. A final cross-sectional PCR (along with DBS and serum sampling) will be performed at study end. This will require the PCR lab to provide timely aggregated reports of first infection event counts (across Group 1 plus 4 and Group 2 plus 5) and may result in more than the required first infection events for either the primary or secondary endpoint.

4.2.1. Primary Endpoint

The primary endpoint is defined as the time to first PCR-detectable malaria infection in Groups 1 and 4 during the ADI phase of the study.

Vaccine efficacy in African adults (Group 1) administered RTS,S with sub-clinical PCR-positive parasitemia at baseline and treated to clear parasites before immunization will be compared to

volunteers in Group 4 with sub-clinical PCR-positive parasitemia at baseline and treated to clear parasites before immunization with a comparator rabies vaccine.

4.2.2. Secondary Endpoints

Secondary endpoint for vaccine efficacy:

The secondary endpoint is defined as the time to first PCR-positive malaria infection in Groups 2 and 5 during the ADI phase of the study. Vaccine efficacy in African adults administered RTS,S, and who are negative for *P. falciparum* infection at baseline and given anti-malaria chemoprophylaxis (Group 2) are compared to rabies vaccinated adult subjects who are negative for *P. falciparum* infection at baseline and given anti-malaria chemoprophylaxis (Group 5).

Secondary endpoint for safety:

- Frequency count and proportion of subjects reporting serious adverse events (SAEs) during the whole study period
- Frequency count and proportion of subjects reporting solicited local and systemic adverse events within 7 days after each vaccination
- Frequency count and proportion of subjects reporting unsolicited adverse events within 28 days after each vaccination

Secondary endpoint for immunogenicity:

- Anti-circumsporozoite (CS) antibody levels & avidity at time points shown in Appendix F.
- Hepatitis B surface antibody (HBsAb) levels at time points shown in Appendix F.

4.2.3. Exploratory Endpoints

Immune profiling of cell-mediated immune (CMI) responses will be assessed only in subjects administered RTS,S (Groups 1, 2, 3). Subjects in Groups 4 and 5 that are administered the comparator rabies vaccine will not have PBMC collected. The flow cytometric assays will measure T cell, B cell and innate cell markers associated with immune exhaustion. The specific flow cytometric assays to be measured may include but are not limited to T cell markers CD3, CD4, CD8, TCRgD, CD56, CD45RA, CD27, CD25, CD127, CTLA4, PD-1 associated with immune exhaustion. Flow cytometric assays specific for B cells, Monocyte, NK subsets may include but are not limited to, CD27, HLA-DR, CD16, CD14, CD123, PD-1, CD56, CD21.

Whole blood samples will be collected for future use to measure RNA transcriptional responses related to innate immune responses before and after immunization as shown in Appendix F. While PAXgene tube samples will be collected from all subjects in Groups 1 through 5, it is anticipated that a small cross-sectional case-control subset of samples may be selected to measure transcriptional immune responses. No genetic testing related to risk of disease will be performed from these samples.

Anti-rabies antibody levels in the first 50 subjects in Groups 4 and 5 will be assayed at timepoints indicated in Appendix F.

HLA typing from buccal swabs or from PBMC will be collected for determination of an association of RTS,S elicited immune responses and protection from *P. falciparum* infection.

The results from the immunological and transcriptional analyses will inform whether the presence or absence of *P. falciparum* infection is associated with immune exhaustion and will serve as a knowledge base for the development of improved second-generation CS-based vaccines.

Malaria parasitemia will be assessed in Groups 1 through 5 at the Study Termination Visit within a 6 week period to get a cross-sectional malaria prevalence.

5. STUDY ENROLLMENT AND WITHDRAWAL

5.1. Participant Inclusion Criteria

In order to be eligible to participate in this study, an individual must meet all of the following criteria:

- Provision of signed or thumb printed and dated informed consent form
- Stated willingness to comply with all study procedures and availability for the duration of the study
- Male or female between 18 and 55 years of age, inclusive
- In good general health as evidenced by medical history and clinical examination before entering the study
- Ability to take oral medication and be willing to adhere to the medication regimen
- For females, she must be of non-childbearing potential or use appropriate measures to prevent pregnancy for 30 days prior to vaccination through 2 months after completion of the vaccine series. Non-childbearing potential means she is surgically sterilized or at least one year post-menopausal. Appropriate measures to prevent pregnancy include abstinence or adequate contraceptive precautions (e.g. intrauterine contraceptive device; oral contraceptives; diaphragm or condom in combination with contraceptive jelly, cream or foam; Norplant or Depo-Provera). Kombewa clinical staff will assist with provision of acceptable birth control for study entry and will discuss with volunteer at screening visit.

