2.3.1.4. Risks of receipt of Primaquine

Subjects who receive primaquine may experience abdominal pain, nausea, vomiting, diarrhea, dizziness, pruritis, and anemia. Standard dose primaquine is contraindicated in subjects with severe glucose-6 phosphate dehydrogenase (G6PD) deficiency due to the risk of hemolytic anemia. However, a single low dose (15 mg primaquine base) is safe in individuals with G6PD deficiency and recommended by the WHO for the clearance of sexual stage gametocytes of *P. falciparum* without specific testing for G6PD in

adults (except in pregnant or breastfeeding women)
[https://www.who.int/malaria/publications/atoz/who_hm_gmp_2015.1.pdf?ua=1].

Primaquine is contraindicated in pregnant women. A single low dose 15 mg base of primaquine will be given under the supervision of a medical provider at KCRC. Any subjects who are unwell at these visits will be referred to a study clinician for evaluation and treatment. G6PD status will not be considered in the context of low dose primaquine administration though testing will be performed in the context of assessing the role of hemoglobinopathies that may impact time to infection detection after an infective mosquito bite.

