4. STUDY DESIGN AND ENDPOINTS

4.1. Description of the Study Design

Tables 1 and 2 above show the groups, sample size, and descriptors.

The study design includes five groups.

Group 1. Group 1 subjects have detectable *P. falciparum* parasitemia at baseline measured by PCR (note any positive result from PCR, per our lab derived cutoff in accordance to the PCR SOP, will be considered positive for purposes of group selection and study endpoints). Anti-malarial treatment with DHA/Pip to clear asexual stage and young gametocyte parasites plus LD PQ to clear mature gametocytes will be given 4 weeks prior to immunization with RTS,S/AS01_E. A 2nd course of DHA/Pip plus Primaquine will be given 2 weeks before second RTS,S/AS01_E immunization. One week before 3rd RTS,S/AS01_E immunization, a three-day course of A/L plus Primaquine will be administered to

clear infection. Rationale for administration of A/L is its preferred shortened half-life allowing for evaluation of vaccine efficacy thereby excluding any confounder effect due to prolonged anti-malarial effect of drug.

Group 2. Group 2 subjects have no detectable *P. falciparum* parasitemia as measured by PCR at enrolment. It is proposed to initiate anti-malarial chemoprevention to subjects (prophylaxis effect) with DHA/Pip plus LD PQ 4 weeks prior to immunization with RTS,S/AS01_E. A 2nd course of DHA/Pip plus Primaquine will be given 2 weeks before second RTS,S/AS01_E immunization. One week before 3rd RTS,S/AS01_E immunization, a three-day course of A/L plus Primaquine will be administered to clear infection.

Group 3. Group 3 subjects have detectable *P. falciparum* parasitemia at baseline measured by PCR but will not receive any anti-malarial medications to clear PCR-positive parasites. This group includes 35 subjects and is included only for immunological assessment and not for vaccine efficacy. Subjects in Group 3 will be administered RTS,S/AS01_E three times on a 0, 1, 7 month schedule.

Group 4. Group 4 subjects have detectable *P. falciparum* parasitemia at baseline measured by PCR (note any positive result from PCR will be considered positive for purposes of group selection and study endpoints as with Group 1) and will receive DHA/Pip, Primaquine, and A/L on the same schedule as subjects in group 1. Subjects in Group 4 will be administered Abhayrab rabies vaccine on a 0, 1, 7 month schedule.

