- Acute or chronic, clinically significant pulmonary, cardiovascular (including cardiac arrhythmias), hepatic or renal functional abnormality, as determined by medical history, physical examination or laboratory screening tests.
- History of homozygous sickle cell disease (Hgb SS).
- Any clinically significant laboratory abnormalities as determined by the investigator on screening labs (site reference ranges, Appendix G).
- History of splenectomy.
- Administration of immunoglobulins, blood transfusions or other blood products within the three months preceding the first dose of study vaccine or planned administration during the study period.
- Pregnant (i.e. a positive pregnancy test) or lactating female during immunization phase of the study (refer to section 2.3 for rationale). If a woman becomes pregnant after all vaccinations are complete, she will not be excluded from the remainder of the study.
- Female planning to become pregnant or planning to discontinue contraceptive precautions during the vaccination phase.
- History of chronic alcohol consumption and/or drug abuse.
- Chronic administration (defined as more than 14 days) of immunosuppressants or other immune-modifying drugs within six months prior to the first vaccine dose (for corticosteroids, this will mean prednisone, or equivalent, $\geq 0.5 \text{ mg/kg/day}$. Inhaled and topical steroids are allowed).
- Major congenital defects or serious chronic illness.
- Simultaneous participation in any other clinical trial (apart from participation in the HDSS network).
- Any other findings that the investigator feels would increase the risk of having an adverse outcome from participation in the trial.

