7.2.1. Clinical Laboratory Evaluations

The clinical laboratories of USAMRD-A will conduct the following testing: CBC (Hb, WBC, PLT), creatinine, ALT, HIV, hemoglobinopathy panel (sickle cell, G6PD, alpha thalassemia), and urine pregnancy testing. These labs will be primarily performed at KCRC clinical labs or the USAMRD-A Basic Science Lab in Kisumu, but other USAMRD-A labs (e.g., Kericho Field Station) or commercial laboratories (e.g., Pathologists Lancet Kenya or PathCare Kenya) are available for back-up testing if the primary laboratories are not available.

A urine pregnancy test must be done in all females of child-bearing potential no more than 24 hours prior to study intervention as indicated in Appendices A & B and the results must be available prior to administration of study products (DHA/Pip, Coartem, Primaquine, RTS,S, Abhayrab).

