APPENDIX B. EPOCH 1: TREATMENT AND IMMUNIZATION PHASE

Visit #	Treatment and Immunization Phase (Epoch 1)																
	2	3^	4^	5	6	7	8^	9^	10^	11	12 ¹	13	14^	15^	16^	17	18 ¹
Type of Visit (KC or FV) preferred	KC	FV	FV	KC	KC	KC	KC	FV	FV	KC	FV	KC	KC	FV	FV	KC	FV
Study day	-27	-26	-25	1	2	8	15	16	17	29	36	57	190	191	192	197	204
Permissible window (+/- days)*	2	0	0	3	0	+2	2	0	0	3	+2	3	2	0	0	3	+2
Issue subject's identification card	•																
Check inclusion/exclusion criteria	•			•			•			•			•				•
Record any intercurrent medical conditions	•			•			•			•			•				•
Record any concomitant medications/vaccinations	•			•	•	•	•	•		•		•	•				•
Record if subject belongs to reactogenicity sub-cohort ¹	•																
Check contraindications to vaccinations/anti-malarial medications	•			•			•			•			•				•
History of fever/Record body temperature	•			•			•			•			•				•
Focused/Symptom & physical exam as needed				•						•							•
DHA/piperaquine	•	•	•				•	•	•								
Primaquine (low dose)	•						•					•					
Coartem												•	•	•			
Record vital signs (BP, pulse, temperature)				•						•							•
Randomization upon completion of parasite PCR	•																
Vaccination				•						•							•
LABS																	
Complete blood count (Hb, WBC, PLT; 4 mL)				•													
Creatinine, ALT (4 mL)				•													
Hemoglobinopathy screen (4 mL)	•																
Urine Pregnancy test	•			•			•			•			•			•	
Buccal swab- HLA typing (Groups 1, 2, 3 only)	• ³																

Visit #	Treatment and Immunization Phase (Epoch 1)																
	2	3^	4^	5	6	7	8^	9^	10^	11	12 ¹	13	14^	15^	16^	17	18 ¹
Type of Visit (KC or FV) preferred	KC	FV	FV	KC	KC	KC	KC	FV	FV	KC	FV	KC	FV	FV	KC	FV	
Study day	-27	-26	-25	1	2	8	15	16	17	29	36	57	190	191	192	197	204
SAFETY DATA COLLECTION ¹																	
Record solicited local & systemic AEs				●	●	●				●	●					●	●
Record unsolicited AEs post anti-malarial treatment/ post vaccination	●	●	●	●	●	●	●	●	●	●	●	●	●	●	●	●	●
Record AEs/SAEs (fatal; AESI)	●	●	●	●	●	●	●	●	●	●	●	●	●	●	●	●	●
INVESTIGATIONAL ASSAYS																	
Blood serum sampling (10 ml) -refer to Appendix F for Group-specific timepoints ²	●			●						●		●				●	
CMI- PBMC from all RTS,S vaccinated subjects Groups 1,2,3 (30 mL)	●			●		●											
Whole blood transcriptomics all subjects (Paxgene; < 3 mL)	●			●	●	●											
PARASITEMIA ASSESSMENT																	
Blood sampling for PCR and DBS (0.35 to 0.5 ml)				●						●						●	

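### The contraception criterion counts 30 days back from vaccination, so on the nominal schedule it requires only about 2 days of cover before the first dose of primaquine, which the protocol calls contraindicated in pregnancy

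*Protocol*

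**What the plan says.** Section 5.1 of the protocol makes it an inclusion criterion that a woman able to conceive should, in its terms, "use appropriate measures to prevent pregnancy for 30 days prior to vaccination through 2 months after completion of the vaccine series". The anchor is vaccination, and the criterion does not name the antimalarial drugs. The same item adds that clinic staff will help with contraception in time for study entry and discuss it at screening, without giving a start date.

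Vaccine is not the first product in four of the five groups. Section 4.1 says of Group 1 that DHA/Pip plus low-dose primaquine "will be given 4 weeks prior to immunization with RTS,S/AS01_E", and of Group 2 that chemoprevention starts "with DHA/Pip plus LD PQ 4 weeks prior to immunization with RTS,S/AS01_E". Groups 4 and 5 follow the schedules of Groups 1 and 2. The day row of Appendix B begins "Study day -27 -26 -25 1 2 8 15". Its first entry is Visit 2, where both drugs are started (window ±2 days), and its fourth is Visit 5, where Dose 1 of vaccine is given (window ±3 days). Group 3 has no scheduled antimalarials.

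On the drug itself, section 2.3.1.4 states: "Primaquine is contraindicated in pregnant women". Pregnancy tests are scheduled at screening and, under section 7.1.1 B and Appendix B, before each antimalarial course and each vaccine dose. Section 7.2.1 requires the test "no more than 24 hours prior to study intervention as indicated in Appendices A & B", with the result available before any listed product, including DHA/Pip and primaquine, is given.

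**The concern.** The criterion is built around vaccine exposure, while the earlier exposure, to the drug the protocol itself calls contraindicated, falls near the start of the required period. Before vaccine the protocol asks for a same-day or previous-day test and 30 days of contraception. Before primaquine it asks for the same test and, in effect, about two days. Nothing in the document explains the difference. The rationale for excluding pregnancy in section 2.3 speaks of the absence of reproductive toxicology for RTS,S/AS01_E and of the study's purpose, and does not mention the antimalarials.

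What is at stake is mainly participant protection. A woman could satisfy section 5.1, test negative at Visit 2 and receive primaquine in a pregnancy not yet detected. The next scheduled test is at Visit 5. Under section 5.4.2 she would then have no further immunizations and, having already received study product, would not be replaced. The loss to the analysis is small; the gap in the rule is the substance of the point.

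**Working it through.** No sample-size or error-rate figure bears on this. The check is calendar arithmetic on the protocol's own schedule.

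**Inputs**
- Required contraception: from 30 days before vaccination (section 5.1).
- First DHA/Pip plus primaquine: Visit 2, day -27, window ±2, so day -29 to day -25 (Appendix B).
- Dose 1 of vaccine: Visit 5, day 1, window ±3, so day -2 to day 4 (Appendix B).
- Screening: day -39 to day -28 (section 7.1.1 A, Appendix A).

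**Step 1: reproduce the stated interval.** Drug to vaccine = 1 - (-27) = 28 days, which matches the four weeks in section 4.1. This counts a day 0. If the numbering has no day 0, the interval is 27 days.

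**Step 2: nominal cover before the first primaquine dose.** Cover = 30 - interval.
- With a day 0: 30 - 28 = 2 days. Equivalently, 1 - 30 = day -29, and -27 - (-29) = 2.
- Without a day 0: 30 - 27 = 3 days.

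**Step 3: extremes of the permitted windows (with a day 0).**
- Latest Visit 2, earliest Visit 5: interval = -2 - (-25) = 23 days; cover = 30 - 23 = +7 days.
- Earliest Visit 2, latest Visit 5: interval = 4 - (-29) = 33 days; cover = 30 - 33 = -3 days, meaning that the required period would begin three days after the drug.
- Without a day 0 the range is -2 to +8 days.

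**Step 4: how much of the window grid is affected.** Five possible days for Visit 2 and seven for Visit 5 give 5 × 7 = 35 whole-day combinations. With a day 0, 10 of 35 give zero or negative cover and 20 of 35 give 2 days or fewer. Without a day 0 the counts are 6 and 15. These count combinations. They are not probabilities, since the documents do not say how visits fall within the windows.

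**Step 5: does screening supply the lead time?** For a woman who starts contraception on the day she is screened:

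| Screened on | Days before drug (day -27) | Days before vaccine (day 1) |
|---|---|---|
| day -39 | 12 | 40 |
| day -28 | 1 | 29 |

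The screening window thus gives 1 to 12 days before the nominal first dose. A woman who starts on day -28 also falls one day short of the 30-day criterion itself. Appendix B has eligibility checked at Visit 2, when nominally only 2 of the 30 required days have passed.

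**The case against.** The strongest reply is that the protocol manages the primaquine contraindication by testing. A woman is tested at screening and again within 24 hours before the first course, the result must be in hand, and section 5.2 excludes anyone who tests positive. Section 5.1 also expects contraception to be arranged for study entry, which a reasonable site would take to mean by Visit 2. And the vaccine anchor agrees with the reason the protocol gives for excluding pregnancy. On this view no two passages contradict each other: nominally, the required period does begin before the drug.

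Much of that stands. The tests and the help at screening are real, though partial, safeguards. The documents give no figure for how early in pregnancy the urine test turns positive, so the remaining risk cannot be sized. But the protocol does not treat a test alone as enough before vaccine, and it nowhere says why it should be nearly enough before primaquine. The study-entry wording carries no minimum duration.

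Four stronger readings are tempting and not supported:
- **That compliant women have no cover at all.** This needs unfavourable combinations of visit windows and sits badly with the study-entry wording. The fair statement is about 2 days nominally, with the range shown.
- **That both drugs are contraindicated.** The protocol says this of primaquine only.
- **That 584 people are exposed.** Groups 1, 2, 4 and 5 total 2 × 164 + 2 × 128 = 584, but that includes men, women of non-childbearing potential and women already using contraception.
- **That sections 5.1 and 5.2 conflict on when the requirement ends.** Section 5.2 excludes a "Female planning to become pregnant or planning to discontinue contraceptive precautions during the vaccination phase", while section 5.1 runs to two months after the series. A participant must satisfy every inclusion criterion and meet no exclusion criterion, so both apply and the longer requirement in section 5.1 governs. The wording overlaps without contradiction.

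**Conclusion.** The point holds in a limited form. As written, the contraception criterion requires about 2 days of cover before the first primaquine dose on the nominal schedule (3 if there is no day 0), and from -3 to +7 days within the permitted windows, against 30 days before vaccine. This rests on reading vaccination in section 5.1 as Dose 1 and on the visit days in Appendix B. It concerns women of childbearing potential in Groups 1, 2, 4 and 5. Their number is not given, and those actually affected are likely to be few. The effect on the efficacy comparisons is negligible beside the 10% dropout already assumed in section 10.5. It is worth correcting as a participant-safety gap in a stated rule, and correction is cheap. The documents do not show that the tests in place are inadequate, nor what lead time would be adequate.

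**What to change.** Reconcile section 5.1 with sections 2.3.1.4, 4.1 and 7.2.1 and with Appendix B, so that the contraception criterion expressly addresses the Visit 2 antimalarial course. Section 7.2.1 already ties the pregnancy test to each study product, which makes the silence of section 5.1 easy to locate. The rule itself, and any interval before the first antimalarial dose, are for the sponsor's clinical team to set. If the present arrangement is intended, the protocol should say so and give the reason. Whatever is chosen should be checked against the day -39 to -28 screening window, so that a woman can meet it and staff can verify it when the drug is given.

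The cost is an amendment and matching consent wording. Some women not using contraception at screening might enter later or need rescreening, which section 7.1.1 A already allows once. No change to sample size or analysis follows.

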5.2. Participant Exclusion Criteria

An individual who meets any of the following criteria will be excluded from participation in this study:

- Planned administration/administration of a vaccine not foreseen by the study protocol from within 30 days before the first dose of study vaccine until 30 days after the last dose of study vaccine.†

† In the context of the COVID-19 pandemic, the administration of the COVID-19 vaccine will be allowed as an exception to this exclusion criteria as follows. The study team will work with the participant to attempt to have any COVID-19 vaccine administration occur 30 days or more before or after study vaccinations. When this is not possible, COVID-19 vaccination will be allowed 10 days or more before or after study vaccination. Intervals shorter than 10 days can be allowed on a case-by-case basis in discussion with the sponsor.
- Any prior receipt of any rabies vaccine or experimental malaria vaccine.
- Confirmed or suspected significant immunosuppressive or immunodeficient condition as determined by the investigator, including clinical stage 3 or 4 human immunodeficiency virus (HIV) infection (Appendix H).
- A family history of congenital or hereditary immunodeficiency.

- History of allergic reactions, significant IgE-mediated events or anaphylaxis to previous immunizations.
- History of any neurologic disorders.
- Acute disease (defined as the presence of a moderate or severe illness with or without fever), including acute malaria, at the time of enrolment. All vaccines can be administered to persons with a minor illness, such as diarrhea or mild upper respiratory infection without fever, i.e. temperature $< 37.5^{\circ}\text{C}$ *. Individuals excluded with acute disease, including acute malaria, can become eligible again after complete recovery of the illness, including appropriate treatment as applicable, and can be rescreened at a later date.

* Temperature readings may be taken by site staff either using either oral, axillary, or infrared thermal thermometers during clinic or field visits, while subjects enrolled in the reactogenicity cohort will be supplied with oral thermometers for the purposes of recording their own temperature measurements in the memory aid over 7 days after each vaccination.
- Acute or chronic, clinically significant pulmonary, cardiovascular (including cardiac arrhythmias), hepatic or renal functional abnormality, as determined by medical history, physical examination or laboratory screening tests.
- History of homozygous sickle cell disease (Hgb SS).
- Any clinically significant laboratory abnormalities as determined by the investigator on screening labs (site reference ranges, Appendix G).
- History of splenectomy.
- Administration of immunoglobulins, blood transfusions or other blood products within the three months preceding the first dose of study vaccine or planned administration during the study period.
- Pregnant (i.e. a positive pregnancy test) or lactating female during immunization phase of the study (refer to section 2.3 for rationale). If a woman becomes pregnant after all vaccinations are complete, she will not be excluded from the remainder of the study.
- Female planning to become pregnant or planning to discontinue contraceptive precautions during the vaccination phase.
- History of chronic alcohol consumption and/or drug abuse.
- Chronic administration (defined as more than 14 days) of immunosuppressants or other immune-modifying drugs within six months prior to the first vaccine dose (for corticosteroids, this will mean prednisone, or equivalent, $\geq 0.5 \text{ mg/kg/day}$. Inhaled and topical steroids are allowed).
- Major congenital defects or serious chronic illness.
- Simultaneous participation in any other clinical trial (apart from participation in the HDSS network).
- Any other findings that the investigator feels would increase the risk of having an adverse outcome from participation in the trial.

